7.3.2.3. Confirmed ORR and Confirmed BOR by mRECIST

Under mRECIST, if radiologic imaging shows CR or PR, a tumor assessment should be repeated at a minimum of 4 weeks to confirm the response in order to claim the CR or PR as the confirmed BOR. If there is no second CR or PR tumor assessment, the CR or PR will be unconfirmed. [Table 4](#) lists the scenarios that can occur after an unconfirmed CR or PR and provides a rule for determining the confirmed BOR in each scenario. A sensitivity analysis will be performed for the ORR assessed under mRECIST, in which BOR is determined using unconfirmed PR and CR.

The mRECIST was adapted from RECIST v1.1 to include criteria that accounts for new lesions that can occur in immuno-oncology subjects before the occurrence of an SD, PR, or CR. Under mRECIST, if radiologic imaging shows PD, tumor assessment should be repeated at a minimum of 4 weeks but not more than 6 weeks later to confirm the progression. If there is no second PD tumor assessment in the 4- to 6-week follow-up time, the PD will be defined as unconfirmed. [Table 6](#) lists the scenarios that can occur after an unconfirmed PD in at least 4 weeks and no more than 6 weeks and provides rules for determining whether or not the unconfirmed PD will be counted as an event in the corresponding scenario.

Table 6: Rules for Determining PD Event Status After an Unconfirmed PD Under mRECIST

Event Occurring After Unconfirmed PD in the Confirmation Window (4-6 weeks)	PD Event Status
Subject had EOS/EOT or started new anticancer therapy.	PD will be confirmed as a PD.
Subject had a confirmed PD.	PD will be confirmed as a PD.
Subject had an CR, PR, SD, or NE.	PD will not be considered as a PD and counted as corresponding CR, PR, SD, or NE for the second timepoint only.

Confirmed ORR by mRECIST will be summarized by treatment group and tumor type for the Phase 2 response evaluable population.

7.3.2.4. Unconfirmed ORR and Unconfirmed BOR by mRECIST – Sensitivity and Supportive Analyses for Confirmed ORR and Confirmed BOR by mRECIST

A sensitivity analysis for the ORR assessed under mRECIST will be performed using unconfirmed CRs and PRs. The unconfirmed BOR is defined as the best response recorded postbaseline before and including the first PD, in the order of CR, PR, SD, PD, and NE. For this definition, responses of CR and PR do not need to be confirmed at a subsequent timepoint. In the case of SD, measurements must meet the SD criteria at least once after the date of first dose at a minimum interval of 49 (56 – 7) days. Subjects that fail to meet this criterion will have confirmed BOR of PD if the next available assessment indicates PD or NE if there is no additional assessment available.

Unconfirmed ORR as assessed by mRECIST will be summarized by treatment group and dose level for the Phase 1 response evaluable population and by treatment group and tumor type for the Phase 2 response evaluable population.

7.3.3. Duration of Response

Duration of response will be assessed with RECIST v1.1 and mRECIST criteria.

Censoring of DOR will follow the same algorithm as the censoring of PFS ([Table 7](#)). Kaplan-Meier curves for DOR will be presented by cohort-specific tumor types. The KM estimate of median DOR will be presented with its 95% CI. The 95% CI will be calculated using Brookmeyer and Crowley's method ([Brookmeyer and Crowley 1982](#)). A swim plot for DOR will be generated under both RECIST v1.1 and mRECIST criteria.

Duration of response as assessed by RECIST v1.1 and mRECIST will be summarized by treatment group and dose level for the Phase 1 response evaluable population and by treatment group and tumor type for the Phase 2 response evaluable population.

7.3.3.1. Duration of Response by RECIST v1.1

Under RECIST v1.1, for unconfirmed objective responders, DOR is defined as the time from the first overall response contributing to an unconfirmed objective response (CR or PR) to the earlier of the subject's death from any cause or first assessment of PD.

7.3.3.2. Duration of Response by mRECIST

Under mRECIST, for unconfirmed objective responders, DOR is the time from the first unconfirmed overall response contributing to an unconfirmed objective response (CR or PR) to the earlier of the subject's death from any cause or first confirmed assessment of PD. Note that the criteria for the assessment of PD in DOR are the same with ORR, which are presented in Section [7.3.2.3](#).

7.3.4. Duration of Disease Control and Disease Control Rate

Duration of disease control (CR, PR, and SD) is defined as the time from the first report of SD or better until disease progression or death from any cause, if occurring sooner than progression, as determined by investigator assessment of radiographic disease per RECIST v1.1 and mRECIST. Note that the criteria for the assessment of PD in duration of disease control are the same with ORR, which are presented in Section [7.3.2.3](#).

The duration of disease control will be estimated with 95% CIs overall and by treatment group. Confidence intervals will be calculated based on the exact method for binomial distributions. Swim plots for duration of disease control will be generated separately for RECIST v1.1 and mRECIST criteria.

Disease control rate, defined as the proportion of subjects who have disease control (CR + PR + SD), as per RECIST v1.1 and mRECIST will be summarized. For the determination of DCR, response of CR and PR do not need to be confirmed at a subsequent timepoint. In the case of SD, measurements must meet the SD criteria at least after the date of first dose at a minimum of 49 days. Subjects who fail to meet this criterion will have confirmed BOR of PD if the next available assessment indicated PD or NE if there is no additional assessment available. Disease control rate will be estimated with 95% CIs.

Duration of disease control and DCR as assessed per RECIST v1.1 and mRECIST will be summarized by treatment group and dose level for the Phase 1 response evaluable population and by treatment group and tumor type for the Phase 2 response evaluable population.

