9.4.1.2. Secondary Efficacy Analyses

Disease control rate, defined as the proportion of subjects who have disease control (CR + PR + SD), as per RECIST v1.1 will be summarized.

Progression-free survival, DOR, and duration of disease control will be estimated using the Kaplan-Meier method as per RECIST v1.1.

In Phase 2, the proportion of subjects who meet the objective response criteria (CR + PR) per RECIST v1.1 will be summarized by tumor type.

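### SAP 7.3.4 gives duration of disease control, a censored time, an exact binomial interval with no estimator or censoring rule, and points its RECIST v1.1 progression to mRECIST rules; DCR is left with no interval method

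*SAP*

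**What the plan says.** SAP 7.3.4 covers two endpoints. Duration of disease control runs from the first SD or better to progression or death, under RECIST v1.1 and mRECIST. Of this duration the section says "The duration of disease control will be estimated with 95% CIs overall and by treatment group", and the next sentence is "Confidence intervals will be calculated based on the exact method for binomial distributions". It names no estimator and no censoring rule. On progression it says that "the criteria for the assessment of PD in duration of disease control are the same with ORR" and refers to Section 7.3.2.3. DCR, the second endpoint, is a proportion; the section says only "Disease control rate will be estimated with 95% CIs".

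The other texts that bear on this are:

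- Protocol 9.4.1.2: "Progression-free survival, DOR, and duration of disease control will be estimated using the Kaplan-Meier method as per RECIST v1.1".
- SAP 7.3.3, for DOR: "Censoring of DOR will follow the same algorithm as the censoring of PFS" (that is, Table 7), and "The KM estimate of median DOR will be presented with its 95% CI", by the Brookmeyer-Crowley method.
- SAP 7.3.3.1: DOR under RECIST v1.1 runs "to the earlier of the subject's death from any cause or first assessment of PD". The reference to 7.3.2.3 appears only in 7.3.3.2, which is the mRECIST definition of DOR.

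**The concern.** Duration of disease control is a time-to-event variable. Some subjects will leave observation without progression; Table 7 lists such cases for PFS, including new anticancer treatment and discontinuation for toxicity. An exact binomial interval applies to a count of successes out of a fixed number. As written, 7.3.4 therefore pairs the endpoint with a method that does not fit it, and supplies neither the estimator nor the censoring rule that would let a programmer do something else.

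The progression reference adds a second problem. Read literally, it sends a RECIST v1.1 duration to rules under which a first PD can be set aside.

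The text is still in force. SAP 2.1 keeps the SAP effective for later protocol amendments unless it is superseded, and Protocol Section 9 limits the work to Phase 1 analyses. Tables 2.1.1.1 and 2.1.1.2 (SAP Appendix A) report duration of disease control beside DOR, both under RECIST v1.1. Two neighbouring results could then rest on different event and censoring rules without the reader knowing.

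**Working it through.** The documents give no numerical result for this endpoint, so there is no figure to reproduce. The check is a comparison of the texts, followed by two single-subject illustrations.

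**What is specified for each endpoint**

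| | PFS (SAP 7.3.7) | DOR (SAP 7.3.3) | Duration of disease control (SAP 7.3.4) | DCR (SAP 7.3.4) |
|---|---|---|---|---|
| Type | time to event | time to event | time to event | proportion |
| Estimator in SAP | Kaplan-Meier median | Kaplan-Meier median | none | proportion |
| 95% CI method | Brookmeyer-Crowley | Brookmeyer-Crowley | exact binomial | none named |
| Censoring | Table 7 | Table 7 | none | not needed |
| RECIST v1.1 progression | first PD | first PD | refers to 7.3.2.3 | not needed |

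The exact binomial entry sits under the wrong endpoint. Moving it one column to the right fills the DCR gap and removes the misfit.

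**Scope.** Six planned tables name this endpoint. Four are Phase 2 (2.1.2.1, 2.1.2.2, 2.1.3.1, 2.1.3.2) and fall away. Two are Phase 1 (2.1.1.1, 2.1.1.2) and remain.

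**Illustrations.** Inputs: scans every 8 weeks (Protocol 7.7.1.1.2); the 4 to 6 week confirmation window and Table 6 (SAP 7.3.2.3); Table 7 (SAP 7.3.7). Durations count from the first SD scan at Week 8, as (week of end point − 8) × 7 days, ignoring the one-day convention. Both subjects are invented, and nothing is claimed about how often they would occur.

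(a) *Progression rule.* SD at Week 8, PD at Week 16, SD on a repeat scan at Week 20 to 22.
- First PD under RECIST v1.1: event at (16 − 8) × 7 = 56 days.
- Table 6: the PD is not counted, so there is no event and the duration is at least (20 − 8) × 7 = 84 to (22 − 8) × 7 = 98 days.

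(b) *Censoring rule.* SD at Week 8, Week 16 and Week 24 scans missed, PD at Week 32.
- Table 7, progression after more than one missed assessment: censored at the last valid scan, (8 − 8) × 7 = 0 days.
- No censoring rule: could be counted as an event at (32 − 8) × 7 = 168 days.

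**DCR.** The choice of interval method is visible at Phase 1 cohort sizes. For an assumed 2 of 6 subjects with disease control, the exact (Clopper-Pearson) interval is 4.3% to 77.7% and the Wilson interval is 9.7% to 70.0%.

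**The case against.** The strongest reply has four parts.

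1. *The Protocol supplies the estimator.* Protocol 9.4.1.2 names Kaplan-Meier, the SAP says it details the Protocol's analyses, and SAP 10.1 records no changes to them. This stands as far as it goes: the missing estimator is a gap in the SAP only. The Protocol gives no censoring rule and no interval method for the endpoint, so the gap is not closed.

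2. *The mRECIST rules limit themselves.* The progression rules in 7.3.2.3 and the title of Table 6 say they apply under mRECIST, and RECIST v1.1 progression is defined elsewhere in the SAP. A careful programmer would probably use first PD, so illustration (a) shows what a literal reading permits and not what must happen. But the note in 7.3.4 carries no such limit and covers both criteria, whereas the DOR sections keep them apart.

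3. *A binomial interval for a duration does exist.* Order statistics give one for an uncensored median. This is true, but the SAP does not name that method, and it fails under censoring. In a simulation with assumed exponential durations (median 4 months), 20 subjects and 30% censored, its coverage was 80.4%, against 92.4% for Kaplan-Meier with Brookmeyer-Crowley limits. Those inputs are assumptions, and the conclusion does not depend on them.

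4. *One misplaced sentence is counted twice, and the table shells are unseen.* The wrong duration interval and the unnamed DCR method probably are one drafting slip. The shells are in a separate document and might show the intended statistic. The point is therefore limited to the text of 7.3.4.

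**Conclusion.** The concern holds. SAP 7.3.4 states an interval method that does not apply to a censored duration, omits the Kaplan-Meier estimator that the Protocol names, has no censoring rule for the endpoint, and points RECIST v1.1 progression to a section written for mRECIST, which Protocol 1.5.4.1.1 says is no longer an endpoint. DCR in the same section has no named interval method. That the binomial sentence was meant for DCR is an inference, though a likely one.

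The size is small. Two live Phase 1 tables carry the endpoint, it is secondary, and Protocol 9.3 calls the study exploratory with no formal tests. No test, error rate, power or dose decision changes. What is at stake is whether the reported durations and their intervals are defined before the data are analysed.

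**What to change.** In SAP 7.3.4:

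1. For duration of disease control, specify the Kaplan-Meier median with a 95% CI by the Brookmeyer-Crowley method, censoring as in Table 7, and progression as the first PD under RECIST v1.1. The two Table 7 rows that censor at Day 1 will not arise, because a subject with a duration has a baseline scan and at least one valid later scan.
2. Limit the reference to 7.3.2.3 to any mRECIST analysis that is kept.
3. Move the exact binomial sentence to DCR.

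The cost is a few sentences of SAP wording. Every method is already in the SAP: the first three for DOR and PFS, and the exact binomial method in 7.3.4 itself. No new data or programming approach is needed.

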7.3.5. Largest Percentage Reduction in Sum of Diameters of Target Lesions

For each subject in the FAS population with target lesions at baseline, target lesion sizes will be measured by sum of diameters. The best percentage change from baseline, defined as the largest decrease in target lesion size for each subject, will be summarized descriptively, and a waterfall plot of the best percentage change will be generated.

Per RECIST criteria, target lesions considered "too small to measure" will be assigned a default value of 5 mm for purposes of this analysis. Likewise, target lesions identified as "not present" at postbaseline assessments will be assigned 0 mm for this analysis. In the event a target lesion is unaccounted for in a particular postbaseline timepoint (ie, assessment missing or NE), then the overall sum of diameters for target lesions will not be evaluable for that postbaseline timepoint.

7.3.6. Percentage Change in Sum of Diameters of Target Lesions Over Time

For each subject in the FAS population with target lesions at baseline, target lesion sizes will be measured by sum of diameters. The percentage change in sum of diameter of target lesions over time will be listed and a spider plot will be generated.

7.3.7. Progression-Free Survival

Progression-free survival is defined as the length of time between the baseline visit (Day 1) and the earlier of death or PD as assessed by RECIST v1.1 and mRECIST. Date of death will be determined using the Death Report CRF, and analyses will be summarized for the FAS population.

Censoring for PFS will follow the algorithm outlined in [Table 7](#) which is based on the FDA Guidance for Industry: Clinical Trial Endpoints for the Approval of Cancer Drugs and Biologics ([FDA 2007](#)).

Kaplan-Meier curves for PFS will be presented by cohort-specific tumor types. The KM estimate of median PFS will be presented with its 95% CI. The 95% CI will be calculated using the Brookmeyer and Crowley's method ([1982](#)).

Table 7: Evaluation and Censoring of Progression-Free Survival

Situation	Outcome	Date of Progression or Censoring
No baseline tumor assessments	Censored	Date of Day 1
No valid postbaseline response assessments	Censored	Date of Day 1
Progression documented between scheduled response assessments	Progressed	Date of first overall response of PD
No progression	Censored	Date of last valid radiologic assessment (not NE and not missing)
Study discontinuation for undocumented progression	Censored	Date of last valid radiologic assessment (not NE and not missing)
Study discontinuation for toxicity or other reason	Censored	Date of last valid radiologic assessment (not NE and not missing)
New anticancer treatment started	Censored	Date of last valid radiologic assessment (not NE and not missing).
Death before first progressive response assessment	Progressed	Date of death
Death between adequate response assessments	Progressed	Date of death
Death or progression after more than 1 missed assessment	Censored	Date of last valid radiologic assessment (not NE and not missing) before death

NE = not evaluable.

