2.2.2. Secondary Endpoints

- ORR, defined as the percentage of subjects having CR or PR, will be determined by investigator assessment of radiographic disease assessments per RECIST v1.1.
- DOR, defined as the time from the earliest date of disease response (CR or PR) until earliest date of disease progression or death due to any cause, if occurring sooner than progression, will be determined by investigator assessment of radiographic disease assessments per RECIST v1.1.
- DCR, defined as the percentage of subjects having CR, PR, or SD, will be determined by investigator assessment of a radiographic disease assessments per RECIST v1.1.
- Duration of disease control (CR, PR, and SD) as measured from first report of SD or better until disease progression or death from any cause, if occurring sooner than progression, will be determined by investigator assessment of radiographic disease per RECIST v1.1.
- PFS, defined as the time from the start of combination therapy until the earliest date of disease progression or death due to any cause, if occurring sooner than progression, as determined by investigator assessment of objective radiographic disease assessments per RECIST v1.1.
- Safety and tolerability will be assessed by monitoring frequency, duration, and severity of AEs.

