7.3.7.1. Progression-Free Survival by RECIST v1.1

Under RECIST v1.1, PFS is defined as the length of time between the baseline visit (Day 1) and the earlier of death or first assessment of PD as assessed by RECIST v1.1.

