7.3.8. Overall Survival

Overall survival is defined as the interval between Cycle 1 Day 1 and the date of death due to any cause. Date of death will be determined using the Death Report, the Survival Follow-Up, and the Subject Status CRFs. Subjects who are lost-to-follow-up or still alive at the time of analysis will be right-censored at the earlier of the date that the subject was last known alive and the clinical data cutoff date for the analysis. The last known alive date is defined as the later of the last study visit and the date the subject was last known alive from the Survival Follow-Up and Subject Status CRFs, and the analyses will be summarized for the FAS population.

Kaplan-Meier time to event curves will be presented by treatment groups. Median survival will be estimated using the Kaplan-Meier method. Kaplan-Meier estimates of 1-year and 2-year survival probabilities will be provided. Confidence intervals for median survival time will be calculated using the method of Brookmeyer and Crowley ([1982](#)).

[REDACTED]

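### SAP 7.3.7 names one CRF as the source of the PFS death date where 7.3.8 names three, so a death recorded only on another form could be censored in PFS

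*SAP*

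**What the plan says.** The endpoint itself sets no limit on how a death is recorded. Protocol 2.2.2 gives "PFS, defined as the time from the start of combination therapy until the earliest date of disease progression or death due to any cause". SAP 7.3.7.1 ends PFS at "the earlier of death or first assessment of PD as assessed by RECIST v1.1".

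The source of the death date differs between two adjacent SAP sections:

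- SAP 7.3.7 (PFS): "Date of death will be determined using the Death Report CRF, and analyses will be summarized for the FAS population".
- SAP 7.3.8 (overall survival), also on the FAS: "Date of death will be determined using the Death Report, the Survival Follow-Up, and the Subject Status CRFs".

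SAP Table 7 then assigns outcomes. The row "Death before first progressive response assessment" is an event on the date of death. The row "Death or progression after more than 1 missed assessment" is censored. A subject with no progression and no recognised death is censored at the last valid scan, as is one who started new anticancer treatment.

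SAP 7.3.3 applies the same censoring algorithm to duration of response. Neither that section nor 7.3.4 (duration of disease control) names a CRF for the death date, although death ends both durations.

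**The concern.** The rule that supplies the PFS death date is narrower than the endpoint it serves. The SAP gives no reason for using one form for PFS and three for overall survival in the same subjects. It does not say that every death must also be entered on a Death Report, and it has no step to reconcile the forms.

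A programmer who follows 7.3.7 literally would not see a death held only on the Subject Status form, on a Survival Follow-Up form completed before Amendment 3, or as an adverse event with a fatal outcome. The subject would be censored although the database holds a PFS event. The overlooked deaths would be those that occur without documented progression, and those are the deaths that contribute to PFS in their own right.

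**Working it through.** The documents give no event count or power for PFS, so there is no planned figure to reproduce. The check applies Table 7 to hypothetical subjects and then gives a rough size.

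**Step 1: when does the form matter?** Inputs: imaging every 8 weeks (56 days) in the first 12 months (Protocol Table 12), so scans fall on Days 57, 113 and 169; censoring rows from SAP Table 7. A scheduled scan strictly before death and not done is counted as missed. The last valid scan is Day 57 throughout.

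| Subject | Death on Death Report | Death on another form only |
|---|---|---|
| No PD, dies Day 90 | Event, Day 90 | Censored, Day 57 |
| PD Day 57, dies Day 90 | Event, Day 57 | Event, Day 57 |
| No PD, new therapy, dies Day 90 | Censored, Day 57 | Censored, Day 57 |
| No PD, dies Day 169 (one scan missed) | Event, Day 169 | Censored, Day 57 |
| No PD, dies Day 170 (two scans missed) | Censored, Day 57 | Censored, Day 57 |
| No PD, dies Day 200 | Censored, Day 57 | Censored, Day 57 |

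The form changes the result only without earlier PD, without new therapy and with at most one missed assessment. The limit is 169 − 57 = 112 days after the last valid scan, that is 2 × 56, ignoring the ±7-day window.

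**Step 2: effect on a median, whole study.** Under an exponential model the estimated median is ln 2 × T/E, with T the total exposure and E the number of events. If k events become censored and T is held fixed, the median is multiplied by E/(E − k). E is not in the documents; 30 to 48 of the 52 subjects is assumed.

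- k = 1: 48/47 = 1.021 to 30/29 = 1.034, so about 2% to 3%.
- k = 3: 48/45 = 1.067 to 30/27 = 1.111, so about 7% to 11%.

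Holding T fixed slightly overstates the effect, because a subject censored at the last scan also contributes less exposure.

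**Step 3: effect in a small group.** Take a hypothetical group of 10: five progress on Day 57, three on Day 113 and one on Day 169; one has stable disease on Day 57 and dies on Day 100.

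- Death counted: 50% at Day 57; 0.5 × 4/5 = 40% at Day 100; 0.4 × 1/4 = 10% at Day 113.
- Death missed, censored at Day 57: 50% until Day 113, then 0.5 × 1/4 = 12.5%.

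The SAP plans a median with its confidence interval for PFS and no rates at fixed times. Both curves reach exactly 50% on Day 57. Under the midpoint convention the median moves from (57 + 100)/2 = 78.5 days to (57 + 113)/2 = 85 days.

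**The case against.** The strongest reply is that 7.3.7 says where the date of death comes from, not which deaths count. The word only does not appear there, and Table 7 has its own row making death before progression an event. If a Death Report is completed for every death, the two sections give identical results. The Survival Follow-Up and Subject Status forms are also needed in 7.3.8 to find the date last known alive, so naming them does not prove that deaths are expected to be missing from the Death Report. The CRFs and their completion rules are not in the documents.

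Most of this stands, and it makes the point conditional. It does not remove it: the Table 7 row needs a death date, 7.3.7 says where that date is taken from, and nothing in either document guarantees that this form is complete.

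Several stronger readings are tempting, but the documents do not support them:

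- A reader might infer that duration of response loses the same deaths through Table 7. SAP 7.3.3 borrows only the censoring table, and the CRF sentence is outside it. For that endpoint the death source is unstated, not restricted.
- A reader might expect subjects to appear dead in the survival table and event-free in the PFS table. Amendment 3 removed overall survival and survival follow-up; the survival analysis remains only in the SAP, whose single version (06 FEB 2018) was written on Amendment 1.
- A reader might call the bias always favourable. From the death date onward a lost death raises the curve, but between the last scan and the death the smaller risk set can lower it slightly.
- A reader might take about 10 subjects per group (52 over five groups) as fact. Enrolment by group is not documented, so the group of 10 is only an illustration.

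**Conclusion.** The two SAP sections name different death sources for the same subjects, and the PFS rule can be narrower in practice than the PFS definition. This is a real inconsistency with a conditional and probably small effect. It bites only if some death is absent from the Death Report, and then only for the narrow set of subjects identified in the check. How many there are cannot be learned from the documents; zero is possible. The percentage effects rest on the assumed event counts and the exponential model.

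It would go too far to say that the plan has been shown to produce informative censoring. PFS is a secondary endpoint in 52 Phase 1 subjects, and Protocol 9.3 foresees no formal tests. The point is worth correcting because the correction is free and can only bring PFS closer to its stated definition.

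**What to change.** In SAP 7.3.7, replace the single-form source with one derived death date taken from every CRF that records death: Death Report, Subject Status, Survival Follow-Up forms completed before Amendment 3, and adverse events with a fatal outcome. Apply the partial-date rule in SAP 4.1.5, which already covers the relevant efficacy endpoints. Use the same variable for duration of response and duration of disease control, so that their death source is stated too.

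An acceptable alternative is to state that a Death Report is mandatory for every death and to reconcile it with the other forms before database lock.

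The cost is one SAP sentence and one derived variable. No new data are needed.
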